7.9.2 Laboratory assessments

Laboratory measurements will be listed and summarized for actual values and change from baseline with descriptive statistics for As-Treated and PSC populations by Timepoint (Day of Implant, Congestion Target Met, Post 72Hrs or Discharge and Follow-Up). Laboratory measurements will be separated into two categories – Blood Labs and Urine Labs.

Additional summary for lactate dehydrogenase (LDH), plasma free Hb (pfH) and urine hemoglobin will be provided for the As-Treated and PSC populations by Timepoint (Day of Implant, Congestion Target Met, Post 72Hrs or Discharge and Follow-Up).

In addition to the collected laboratory measurements, the following derived parameters will be listed and summarized as the part of Urine Labs category (with the Date/Time of measurement and Timepoint as for corresponding Albumin and Creatinine evaluations):

$$\text{UACR (mg/g)} = \frac{\text{Urine Albumin (mg/dL)}}{\text{Urine Creatinine (g/dL)}}.$$

Laboratory measurements (except for Blood Labs evaluations of Blood Urea Nitrogen and Creatinine) collected from the time of implant until Post 72Hrs or Discharge will be presented graphically by patient for As-Treated and PSC populations.

Blood Labs measurements of Blood Urea Nitrogen and Creatinine collected from the time of implant until Follow-Up will be presented graphically by patient for As-Treated and PSC populations.

Boxplots of Blood Urea Nitrogen and Creatinine will be provided by subgroup and overall to compare baseline results with Congestion Target Met and Follow-Up for As-Treated population.

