1.2 Clinical Experience

Procyron completed a first-in-human (FIH) study (n=6) with the Aortix System in the setting of high-risk percutaneous coronary intervention (HR-PCI) procedures.²⁶ The mean number of lesions treated during the procedure was 1.5 (range 1-4).

The Aortix Pump supported the patients during the HR-PCI procedure and was removed at the end of the procedure. The Aortix Pump operated for an average of 70 min (range 47-95) and was deployed in less than 10 minutes in all cases with no device failures. The Aortix Pump operated continuously at an average of 3.5 L/min of estimated pump flow. Angiographic success was achieved in all patients and no episodes of hemodynamic compromise or hemolysis occurred on Aortix Pump support.

Safety, procedural, and efficacy outcomes were assessed. No adverse events or safety issues occurred, and the study generated clinical data suggesting that the Aortix Pump improved both hemodynamics and kidney function.

During therapy, urine output increased an average of 10-fold (n=4 with available data) and serum creatinine decreased an average of 0.12 mg/dL at discharge (n=6) despite contrast load from the HR-PCI procedure.^v Hemodynamics including heart rate and proximal and distal aortic pressures were maintained during and after the HR-PCI procedure.

[figure not shown]
In summary, the Aortix Pump was acutely deployed and retrieved in a simple percutaneous procedure in the setting of HR-PCI (n=6) with 100% angiographic success and no clinical adverse events, adverse device effects, device deficiencies or incidents of hemodynamic compromise were observed. Acute signals from the HR-PCI patient population point to a potential for hemodynamic improvement and a reno-protective effect that could benefit ADHF patients.

2. Device Description

Brief descriptions of the following components of the Procyrion Aortix System are provided below: the Aortix Delivery System, the Aortix Pump, the Aortix Control System, and the Aortix Retrieval System. The Aortix System is investigational. Refer to the Aortix System Instructions for Use (PPL004) for detailed product specifications and instructions for use.

The Aortix Delivery System, Introducer Set and Aortix Pump

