3.6 Subject Withdrawal and Discontinuation

Every effort shall be made to keep all patients in the study for the duration. However, the patient's participation in this study is completely voluntary. If the patient decides not to participate or to withdraw from the study, their decision will have no effect on any services or treatment the patient is currently receiving and will not affect their relationship with their doctor. Additionally, the Principal Investigator may withdraw or choose not to enroll a patient if they feel they do not meet the protocol defined criteria or if it is in the best medical interest of the

^{viii} If patient doesn't have a, b, c, d or f, but the platelet count at time of enrollment is <75,000 cells/mm³, patient can be enrolled and the platelet count re-assessed at the time of the procedure. The platelet count at time of procedure should be ≥75,000 cells/mm³. If platelet count at time of procedure is <75,000 cells/mm³, patient would be a screen failure.

^{ix} Anatomy assessment requires patient to sign informed consent.

patient in question. A patient may also be withdrawn if they have a terminal event, defined as a heart or kidney transplant, death, dialysis, ultrafiltration or CRRT or LVAD implant.

In cases of voluntary patient withdrawal, all data collected from the time of informed consent to the time of voluntary withdrawal may be used. If a patient chooses to withdraw from the study prematurely, the reason for withdrawal will be documented on the applicable electronic case report form (eCRF). If patient requests to withdraw after the investigational Aortix Pump is deployed, the Aortix Pump must be retrieved, and the patient shall be instructed and encouraged to continue follow-up visits for evaluation of the patient's health status.

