2 STUDY DETAILS

2.1 Study Objectives

The **objectives of the study** are:

- Safety:
 - Observe the nature, severity, and frequency of adverse events associated with the delivery, use, and retrieval of the Aortix Pump.
- Performance:
 - Successfully deliver the Aortix Pump to the descending thoracic aorta using the Aortix Delivery System;
 - Aortix Pump shall function as programmed for the duration of therapy;
 - Manage the Aortix Pump Power Lead and access site over the course of therapy without significant complications;
 - Successfully retrieve and remove the Aortix Pump using the Aortix Retrieval System.
- Effectiveness:
 - Evaluate hemodynamic decongestion (CVP, PCWP) during Aortix therapy;
 - Evaluate the effect of the Aortix therapy on kidney function;
 - Evaluate the impact of the Aortix Pump on clinical biomarkers of congestion.

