5.4 Additional Data to be Reported

- Rate of occurrence of all adverse events;
- Utilization of continuous renal replacement therapy (CRRT), ultrafiltration and dialysis;
- Change in serum creatinine;

- Change in eGFR;
- Change in diuretic doses;
- Change in urine sodium excretion;
- QoL changes from KCCQ and EQ5D;
- Change in dyspnea assessment;
- Changes in echo parameters (includes CO);
- Changes in cardiac output and cardiac power output;
- Rates of hemolysis as measured by Lactate Dehydrogenase (LDH), Plasma Free Hb (pfH) and urine hemoglobin.

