6.1.3 As-Treated Population

The As-Treated population will be defined as all enrolled patients with the pump implanted (hemostasis achieved). This population will be used for partial demographic analysis as well as all safety and efficacy analyses.

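### SAP 7.9.2 has no rule for creatinine, BUN and eGFR once a patient is on dialysis or CRRT, so the renal summaries can understate renal worsening

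*SAP*

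**What the plan says.** SAP section 2.1 lists among the effectiveness objectives: "Evaluate the effect of the Aortix therapy on kidney function". Changes in serum creatinine and eGFR are reported under SAP 5.4 as additional data.

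The method is in SAP 7.9.2: "Laboratory measurements will be listed and summarized for actual values and change from baseline with descriptive statistics for As-Treated and PSC populations by Timepoint". The timepoints are Day of Implant, Congestion Target Met, 72 h or discharge, and Follow-Up. The same section adds: "Boxplots of Blood Urea Nitrogen and Creatinine will be provided by subgroup and overall to compare baseline results with Congestion Target Met and Follow-Up". The As-Treated population (SAP 6.1.3) is every enrolled patient with the pump implanted, and starting RRT later does not remove anyone from it.

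RRT is foreseen. Protocol section 3.6 says: "A patient may also be withdrawn if they have a terminal event, defined as a heart or kidney transplant, death, dialysis, ultrafiltration or CRRT", with LVAD implant completing the list. SAP 5.4 promises to report: "Utilization of continuous renal replacement therapy (CRRT), ultrafiltration and dialysis". SAP section 7 gives no method for that item, and Appendix 1 has no table, figure or listing titled for it.

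**The concern.** Dialysis and CRRT clear creatinine and urea from the blood. A value drawn while they run reflects the treatment as well as the kidney, and an eGFR computed from it is not a measure of kidney function. The SAP neither excludes, flags nor reassigns such values. A patient whose kidneys failed badly enough to need RRT can therefore contribute a moderate or even favourable change from baseline. If that patient is withdrawn, the worst renal outcome leaves the later summaries because it was the worst.

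The study has one arm, so no control group would show the artefact, and the SAP says the data will inform the design of later studies (section 2.3). The tables a reader would use to judge the kidney objective would not show how many patients were on RRT.

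**Working it through.** **Text check.** Neither document contains a rule for laboratory values after RRT.

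- SAP section 4 defines baseline and treatment-emergent events only. SAP 7.14 lists one departure from the protocol, on the urine-output timepoint.
- Protocol Appendix A schedules creatinine and eGFR every 24 h after retrieval, at 72 h/discharge and at 30 days. BUN is scheduled at the last two. None of these is conditional on RRT.
- Withdrawal at RRT is permitted, not required, so both routes (pooled value, missing value) are open.
- Exclusion criterion 7 bars dialysis, CRRT or ultrafiltration in the previous 90 days. Baseline values should therefore be free of recent RRT, and contamination falls on the post-implant side.
- Congestion Target Met labs are drawn before the pump speed is turned down (protocol 4.5.3, Appendix A). They are affected only if RRT starts while the pump is running. Exposure is mainly at 72 h/discharge and Follow-Up.

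**Size.** The plan states no figure to reproduce, and its sample size was not statistically derived. What follows is illustration.

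Inputs:
- N = 30 implanted patients (SAP 2.3), all taken as evaluable.
- Assumed: k = patients on RRT, 1 to 6.
- Assumed: d = creatinine change from baseline measured on RRT, -1.5 to +0.3 mg/dL.
- Assumed: w = last pre-RRT change, +1.0 to +2.0 mg/dL.
- Assumed: m0 = mean change in the other patients, 0 to +0.2 mg/dL.

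Formulas:
- Pooled mean = [(30 - k) × m0 + k × d] / 30
- Last-pre-RRT mean = [(30 - k) × m0 + k × w] / 30
- Mean if RRT patients are withdrawn = m0
- Pooled minus last-pre-RRT = k × (d - w) / 30, which does not depend on m0

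Shift per pooled patient:
- Smallest: (0.3 - 1.0)/30 = -0.023 mg/dL
- Largest: (-1.5 - 2.0)/30 = -0.117 mg/dL
- Three patients: -0.07 to -0.35. Six patients: -0.14 to -0.70.

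Mean changes with m0 = +0.1 and w = +1.0 (mg/dL):

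| k | Pooled, d = -1.0 | Pooled, d = +0.3 | Withdrawn | Last pre-RRT |
|---|---|---|---|---|
| 1 | +0.063 | +0.107 | +0.100 | +0.130 |
| 3 | -0.010 | +0.120 | +0.100 | +0.190 |
| 6 | -0.120 | +0.140 | +0.100 | +0.280 |

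For k = 3: pooled = (27 × 0.1 - 3 × 1.0)/30 = (2.7 - 3.0)/30 = -0.010; last pre-RRT = (2.7 + 3.0)/30 = +0.190.

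**Sign.** With m0 = +0.1, the pooled mean becomes an apparent fall once 2 patients (d = -1.5), 3 patients (d = -1.0) or 6 patients (d = -0.5) are on RRT. With m0 = +0.2 the counts are 4, 6 and 9. If creatinine on RRT stays above baseline, the pooled mean does not turn negative, but it still lies below the last-pre-RRT mean. Withdrawal leaves the mean at m0, so it yields an apparent fall only if the remaining patients' own mean is a fall.

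**The case against.** A reader might infer that the SAP will tabulate a renal failure as an improvement. The documents do not support that as a certainty. It requires RRT to occur, study labs to continue, and the on-RRT value to lie below the pre-implant baseline. None of these is established, and the d = +0.3 column shows no false improvement. This part of the objection stands.

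A reader might also set the possible shift against the mean fall of 0.12 mg/dL reported from the first-in-human study (protocol 1.2). That comparison does not hold either. The figure comes from six high-risk PCI patients supported for an average of 70 minutes and is no target for this trial. Matching it requires picking one assumed fall on RRT.

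Nor is RRT hidden from the report as a whole. Protocol Appendix C counts it as AKI Stage 3 whatever the creatinine. Adverse events are summarised by category in the ITT population and listed for all enrolled patients (SAP 7.9.1). Creatinine and BUN are plotted patient by patient to Follow-Up, and protocol section 7 says each patient's data will be reviewed individually. The Follow-up Information table may carry RRT, but its content depends on a CRF that is not available here, so the missing output is shown only at the level of titles. All this is fair, but it leaves the renal summaries and boxplots uncorrected. The protocol accepts that RRT overrides creatinine for classifying AKI; the laboratory section of the SAP does not carry that over.

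Finally, creatinine and eGFR are descriptive additional data, not primary endpoints, and BUN is not in the SAP 5.4 list. That limits the weight of the point without removing it.

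**Conclusion.** The gap is real. Followed as written, SAP 7.9.2 pools values drawn on dialysis or CRRT or loses them through informative withdrawal. Both routes understate renal worsening relative to the last pre-RRT value, provided that value had risen above what would otherwise enter the summary. Apparent improvement is possible, not certain.

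The size cannot be taken from the documents. The range of about -0.02 to -0.12 mg/dL per pooled patient rests wholly on the assumed values of d and w and on 30 evaluable patients. Fewer evaluable patients, as in the HFrEF and HFpEF subgroups, would make each one count for more. The primary effectiveness endpoints are not touched. What is affected is the conclusion that can be drawn about kidney function, which is reason enough to settle the rule before results are seen.

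**What to change.** In SAP 7.9.2, state that:

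- creatinine, BUN and eGFR values obtained while a patient is receiving dialysis or CRRT are excluded from the main summaries and boxplots and flagged in listings and individual plots;
- values obtained after RRT has stopped are kept and flagged, so that true recovery after temporary RRT is not lost;
- each timepoint shows n/N with dialysis, CRRT or ultrafiltration by then, including patients withdrawn for it;
- a sensitivity summary uses the last pre-RRT value for patients on RRT or withdrawn for it;
- the all-observed summary is shown as secondary.

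Add an RRT utilization table to Appendix 1, with a short method in section 7, to deliver what SAP 5.4 promises.

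The n/N line is essential: excluding on-RRT values alone would leave a main summary limited to patients not on RRT. Carrying the pre-RRT value forward to Day 30 for everyone as the main analysis is not advised, because it would hide recovery.

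The cost is SAP wording, a little more programming and one more table, plus a check that RRT start and stop dates are captured. The reported renal change may look somewhat less favourable.

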4.5.1 Initial Data Collection

Following the implant procedure (time zero), the following data will be collected and entered on the eCRFs while the pump is implanted:

- Two (2) hours post implant:
 - Vital signs (HR, BP, RR)
 - Fluid Ins and Outs since last reading
 - Hemodynamics
 - CVP
 - PA Systolic
 - PA Diastolic
 - PA Mean
 - PCWP
 - SvO2 as measured by the PA catheter
 - SaO2 as measured by pulse oximetry
 - Document any medication changes and adverse events
 - Urine labs per Appendix A
- Six (6) hours post implant and every 6 hours for 24 hours post implant:
 - Vital signs (HR, BP, RR)
 - Fluid Ins and Outs since last reading
 - Hemodynamics
 - CVP
 - PA Systolic
 - PA Diastolic
 - PA Mean
 - SvO2 as measured by the PA catheter
 - SaO2 as measured by pulse oximetry
 - Document any medication changes and adverse events
- Twelve (12) hours post implant and every 12 hours until Pump retrieval:
 - Blood and urine labs per Appendix A
- Twenty-four (24) hours post implant and every 24 hours until Pump retrieval:
 - Cardiovascular exam (edema, pulmonary auscultation, weight)
 - Vital signs (HR, BP, RR)
 - Fluid Ins and Outs since last reading
 - Hemodynamics
 - CVP
 - PCWP
 - PA Systolic
 - PA Diastolic
 - PA Mean
 - SvO2 as measured by the PA catheter
 - SaO2 as measured by pulse oximetry

- Dyspnea evaluation
- Document any medication changes and adverse events
- Blood labs per Appendix A

BMI will be calculated by the sponsor. Patient should be maintained on anticoagulation and antiplatelet therapy per **Appendix B**.

If the Aortix Pump is suspected to be malfunctioning or mal-positioned, imaging studies, diagnostic procedures, or access site exam may be performed as needed.

Prior to any unplanned retrieval of the Aortix Pump, hemodynamic and laboratory assessments should be repeated, and a fluoroscopic image of the pump position should be taken, and the image documented.

Refer to **Appendix A** for a detailed study monitoring schedule.

4.5.2 Programming the Aortix Pump/Pump Speed Changes:

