5.2 Potential Risks

The risks associated with trans-femoral interventions and mechanical circulatory support (MCS) are the predominant risks of the study. Most of the risks of the investigational Aortix System procedure are similar to the risks associated with other percutaneous MCS devices. The likelihood of these risks is unknown since the use of MCS in this patient population has not been rigorously studied. These potential risks include, but are not limited to, the following:

- Allergic Reaction or Hypersensitivity
- Aortic Injury (including aortic puncture, tear, dissection or perforation)

- Anemia
- Bleeding (from the access site or due to anticoagulation therapy)
- Bruising at the Access Site
- Death
- Device Failure
- Device Malfunction
- Device Migration or Dislodgment
- Embolism
- Hematoma
- Hemolysis
- Hepatic Injury
- Immune reaction
- Infection
- Insertion Site Hematoma
- Limb Ischemia
- Need for Additional Intervention (Surgical or Non-Surgical)
- Neurological Event
- Nerve Injury
- Pain
- Pump Thrombosis
- Renal Injury
- Sepsis
- Syncope
- Thrombocytopenia
- Thromboembolic Complication
- Thrombotic Vascular Complication
- Vascular Injury (non-Aortic)
- Vascular steal
- Wound Dehiscence

The risks of the investigational Aortix System procedure are similar to the risks listed above; however, the frequency of some may be increased or decreased with the Aortix System procedure or device. For example, the risks of bleeding may be increased by the large diameter Aortix Delivery and Retrieval Systems and the delivery and retrieval procedures, and the risk of infection as compared to the chronic use of IABP or Impella has not yet been established. Other risks, such as hemolysis, may be reduced due to the unique design and fixation of the Aortix Pump.

Given the size of the 18F ID/21F OD Aortix Delivery System and Aortix Retrieval System, potential vascular complications (as listed above) will be carefully monitored. Prior studies of cardiac devices requiring large-bore vascular access have demonstrated higher rates of vascular access complication with increasing size. In the transcatheter aortic valve replacement (TAVR) pivotal trials, major vascular access complications occurred in 5.9%

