	Current hospitalization once	once	2 hours post implant (± 30 min)	Every 12h (± 1 hour)	Every 24 h (± 2 hours)	once	once	Every 24 h (± 2 hours)	Once at 72 hours post retrieval (± 4 hours) or discharge (whichever is earlier)	once
White Blood Cells, Platelets		X		X		X			X	X
Hemoglobin, Hematocrit		X		X		X	X	X	X	X
Sodium, Potassium, CO ₂ , Chloride	X	X		X		X			X	X
Bilirubin (total)	X	X		X		X			X	X
ALP, ALT/SGPT, AST/SGOT	X	X		X		X			X	X
Serum BUN or Urea	X	X		X		X			X	X
Serum Creatinine	X	X		X		X	X	X	X	X
eGFR	X	X		X		X	X	X	X	X
Plasma Free Hb (pfH)*		X			X	X	X	X	X	
LDH *		X		X		X	X	X	X	
aPTT + INR	X	X		X		X			X	
NT-pro-BNP or BNP**		X		X		X	X	X	X	X
Urine sodium (NA ⁺)		X	X	X		X			X	X
Urine creatinine		X	X	X		X			X	X
Urine urea		X	X	X		X			X	X
Urine osmolality		X	X	X		X			X	X
Urine Blood (Hemoglobin)*♦		X		X		X			X	
Urine albumin		X	X	X		X			X	X

*these values will be monitored if the pump speed is adjusted before weaning begins (see protocol section 4.5.2)

**clinical site may report either NT-pro-BNP or BNP for a patient, but should be consistent with all measurements for that patient during the study (do not mix NT-pro-BNP and BNP measurements for a given patient during the study). BNP is the preferred measurement.

⌚ 2 hours from time pump turned on during the deployment procedure.

◆ only required if collected per institution's standard of care urinalysis

α One time assessments to be taken once congestion targets are met or therapy has been deemed ineffective (decision has been made to retrieve device). These assessments should be performed before the pump speed is turned down; within 12 hours of beginning weaning.

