Appendix B: Anticoagulation Protocol

Follow your institution's protocol for percutaneous MCS devices.

The following targets are recommended:

Device Implant:

1. Once sheath is inserted into the femoral artery, administer unfractionated heparin (UFH) to a target ACT of 250 seconds.
2. After insertion of the sheath and until end of pump implantation procedure, ACT should be maintained at 250 seconds.

Anticoagulation Maintenance:

Note: High inter- and intra-patient variability is common with these devices. Selection of the goal anticoagulation range and titration of heparin should be done in the context of the patient's overall clinical status and should include evaluation of all applicable hematologic markers (e.g., aPTT, ACT, platelets, fibrinogen, Hgb, Hct, anti-Xa UFH).

1. Titrate systemic heparin dose to achieve a goal aPTT of 45-60 seconds or a goal Anti-Xa UFH level of 0.5-0.7 IU/mL.
2. Monitor Platelet count daily for Heparin Induced Thrombocytopenia (HIT)
3. If issues with bleeding observed, down titrate heparin/Anti Xa UFH as needed.

Anti-Platelet Maintenance:

1. Patients are to be maintained on any oral anti-platelet therapy they may have been receiving prior to study participation (e.g. aspirin, ticagrelor, prasugrel or clopidogrel).
2. For patients not already on an antiplatelet agent, aspirin (ASA) should be started at a dose such as 81 mg/day within 24 hours after implant if there are no postoperative bleeding complications. The aspirin can be continued until device retrieval.
3. For patients not an alternative antiplatelet agent or who have an aspirin allergy or are otherwise intolerant, clopidogrel 75 mg daily is a viable alternative until device retrieval.

Note: All anticoagulation titrations will be documented on the Aortix eCRF.

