7.14 Changes to Analyses Specified in Protocol

At the time of this SAP preparation, the following changes have been made to analyses specified in the protocol:

- The protocol specifies analysis of change in Urine Output Assessed as the hourly rate of urine output before pump implanted vs hourly rate of urine output over the Aortix therapy period until congestion target met or therapy deemed ineffective. But timepoint “Once Congestion

Target Met” is not collected in the latest CRF. Due to that, the last pre-retrieval timepoint available is used instead of the Congestion Target Met timepoint.

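### Laboratory tables keep one on-pump value out of about 4 to 14 scheduled draws, with no worst value, no patient counts and no rule for early retrievals

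*SAP*

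**What the plan says.** **Collection.** Protocol 4.5.1 schedules blood and urine labs at "Twelve (12) hours post implant and every 12 hours until Pump retrieval". In Appendix A the rows "White Blood Cells, Platelets", "Hemoglobin, Hematocrit" and "ALP, ALT/SGPT, AST/SGOT", and the total bilirubin row, are all marked in the 12-hourly column. Hemoglobin is also drawn in the cath lab before retrieval and every 24 hours afterwards. Platelets, bilirubin and liver enzymes are not; after the pump is out, their next scheduled value is at 72 hours or discharge. Protocol 4.5.1 also asks for labs to be repeated before any unplanned retrieval.

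**Why these tests matter.** Protocol 5.2 lists anemia, bleeding, hepatic injury and "Thrombocytopenia" among the potential risks. Appendix B adds "Monitor Platelet count daily for Heparin Induced Thrombocytopenia (HIT").

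**Tabulation.** SAP 7.9.2 gives actual values and changes from baseline for the "populations by Timepoint (Day of Implant, Congestion Target Met, Post 72Hrs or Discharge and Follow-Up"). SAP 3.2 sets the statistics for continuous variables: mean, median, SD, minimum and maximum. The tables in SAP Appendix 1 include no nadir, peak or threshold-count table for these tests.

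**The on-pump row.** Appendix A defines the Congestion Target Met assessment as made once targets are met or therapy is judged ineffective, with a decision to retrieve. SAP 7.14 says this timepoint "is not collected in the latest CRF" and substitutes the last available pre-retrieval timepoint, for urine output only.

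**The concern.** A laboratory safety table for a device in place for days should show how far each value moved during support and in how many patients. Here the single on-pump row sits at the end of support. A platelet or hemoglobin fall that recovered before that visit, or a transient enzyme rise, leaves no trace in the table.

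The source of the row is also unsettled. If SAP 7.14 applies to labs, the row has no stated source. Whether or not it applies, neither document says which row takes the labs repeated before an unplanned retrieval. Protocol 5.3 foresees retrieval for unsafe therapy, yet the Appendix A definition of the visit does not name a safety retrieval. The patients of most interest may therefore be absent. SAP 3.2 does not list the number of contributing patients among its statistics, so an absence may not show in the table.

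At stake is whether the pilot reports usable on-pump frequencies. Protocol 7 promises event rates and input to the design of later studies. Cut-offs chosen after reading the plots would be post hoc.

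**Working it through.** The plan states no figure on this point, so there is none to reproduce. The check compares the draw schedule with the table rows.

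**1. Draws against tabulated values.** Inputs: one draw per 12 hours (Protocol 4.5.1, Appendix A); a minimum of 2 days at the initial speed (4.5.2.1); device tested for 7 days of use (4.5).

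Scheduled draws = 24 × days / 12.

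| Days on pump | Scheduled draws | Share tabulated if the target-met value is a scheduled draw | Share if it is an extra draw |
|---|---|---|---|
| 2 | 4 | 1/4 = 25% | 1/5 = 20% |
| 4 | 8 | 1/8 = 12.5% | 1/9 = 11% |
| 7 | 14 | 1/14 = 7% | 1/15 = 7% |

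**2. Possible loss from the row.** The documents give no number of safety retrievals, so this is an assumed range. If m of 30 implanted patients are retrieved early and not assigned to the row: 1/30 = 3%, 3/30 = 10%, 5/30 = 17%, 8/30 = 27%.

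**3. Last value against worst value (illustration only).** Assumptions not in the documents: each draw has a 5% chance of lying beyond some limit, values are serially correlated (first-order autoregressive, correlation 0.5 to 0.95), and there are 30 patients.
- Row based on the last draw: 30 × 0.05 = 1.5 patients expected, whatever the duration.
- Any on-pump draw beyond the limit, by simulation: 2.5 to 4.7 patients at 2 days and 4.6 to 12.7 at 7 days.

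The two summaries answer different questions, and the worst-value count grows with time on support.

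**4. Can the adverse event tables stand in?** Appendix C has no definition of thrombocytopenia or hepatic injury, and none of anemia on its own. Its hemoglobin-drop bleeding criteria require overt bleeding. Its hemolysis definitions, which carry the anemia and bilirubin criteria, apply only after the first 72 hours. The first 72/12 = 6 scheduled draws therefore fall outside them, including all 4 draws of a patient supported for 2 days. Protocol 6 leaves it to the investigator whether an abnormal value becomes an adverse event.

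**The case against.** The strongest reply is that nothing is lost. SAP 3.1 puts all data in listings, and SAP 7.9.2 plots these labs for each patient from implant to 72 hours or discharge. With at most 30 implanted patients and individual review promised in Protocol 7, every nadir can be seen. The adverse event definition includes abnormal laboratory findings, bleeding is graded partly by hemoglobin fall, and adverse events are counted by category (SAP 7.9.1). This is a single-arm descriptive pilot, and platelets, hemoglobin and liver tests are not among its endpoints.

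Much of that stands, and it rules out several stronger readings a reader might infer:
- **That on-pump nadirs and peaks are never counted.** Those reported as adverse events are counted, and the rest are visible in plots and listings.
- **That the table works only on a mean scale.** Minimum and maximum are planned, so an extreme present at the target-met visit would show, though not how many patients had one.
- **That patients retrieved for safety drop out.** The visit also covers therapy judged ineffective, and labs are repeated before unplanned retrieval. Such patients may have a value; the mapping is simply unstated.
- **That SAP 7.14 empties the laboratory row.** Its sentence sits in a urine-output item, while SAP 7.8.3 and Listing 16.2.6.4 still rely on the timepoint. The documents conflict, and this would not in itself select the sicker patients.

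What does not stand is that plots and adverse event tables replace a laboratory summary. Step 4 shows why the adverse event route is incomplete, and a plot gives no prespecified count with a denominator.

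**Conclusion.** The point holds as a gap in the summary tables and an unspecified rule for one row, not as a loss of data. Of about 4 to 14 scheduled on-pump draws per patient over 2 to 7 days, one on-pump value is tabulated. No laboratory table gives the on-pump extreme or the number of patients affected for four listed risks. The source of the one on-pump row is unclear after SAP 7.14, and early safety retrievals may be missing from it.

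The draw counts rest on the protocol schedule. The 3% to 27% range for loss from the row and the simulated counts rest on assumed inputs and only illustrate scale. The documents do not show that the planned table will look safer than the truth. The change is worth making before analysis because the data are already collected.

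**What to change.** In SAP 7.9.2 and Appendix 1:

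- **Add one table for all As-Treated patients**, covering pump-on to retrieval and using every scheduled and pre-retrieval draw: platelet nadir, hemoglobin nadir, largest hemoglobin fall from the pre-implant value, and peak bilirubin, ALT and AST. Report retrieval to 72 hours or discharge separately, so that retrieval bleeding is not mixed with on-pump change.
- **Give counts with denominators** at descriptive cut-offs, for example platelets below 75,000 cells/mm³ (the figure in exclusion 17e), hemoglobin falls of at least 3 and at least 5 g/dL, and bilirubin above 2 mg/dL (figures in Appendix C). Label them as counting thresholds only, not adverse event definitions or clinical rules, because the protocol uses them for eligibility, overt bleeding and hemolysis. Show how many patients were already beyond a cut-off before implant.
- **Report duration of support alongside**, since worst values accumulate with the number of draws.
- **Define the on-pump row** as the Congestion Target Met value or, if absent, the last non-missing on-pump value, including labs repeated before unplanned retrieval. State how many patients used the fallback. This follows the last on-therapy value that SAP 7.9.5 uses for the CVP and PCWP boxplots.
- **Reconcile SAP 7.14** with the other sections that use the timepoint.

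Cost: one extra table and a row rule, with no new draws. Worst-of-many values will look less favourable than end-of-support values, rise with time on support and include isolated laboratory outliers, which should be footnoted.
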